4.5.2 Repeated Measurements

If control measurements for the screening visit are available, the last value will be used for the calculation of descriptive statistics. If control measurements for a planned time point except screening are available, the first value (i.e. of the planned measurement) will be used for the calculation of descriptive statistics.

4.6 Blind Review

The results of the final data assessment will be documented in the final list of important deviations, validity findings and assignment to analysis sets. Any changes to the statistical analysis prompted by the results of the review of study data will be documented in an amendment and, if applicable, in the clinical study report (CSR).

5. Analysis Sets

5.1 Assignment of analysis sets

In absence of intervention and randomization the statistical analysis sets are defined as follows:

Full analysis set (FAS) [= Safety analysis set (SAF)]

All subjects that were enrolled into the study and that wore at least one device will be included in the FAS.

Device Set (DES)

All subjects with DynaPort parameters for least one wearing period will be included in the DES.

6. Statistical Methodology

6.1 Population characteristics

If not stated otherwise, analyses will be performed on the FAS population.

6.1.1 Subjects validity, disposition

Study sample size will be summarized by cohort and total, subject validity with reason for exclusion from analysis sets, subject disposition, and important deviations / validity findings will be summarized by total using frequency tables.

6.1.2 Demographics

Summary statistics (arithmetic mean, standard deviation, median, minimum, and maximum for quantitative variables) will be presented by cohort and total. Frequency tables for qualitative data will be provided. If the DES differs from the FAS, summary statistics and frequency tables for DES will be provided as well.

6.1.3 Medical and surgical history

The number of subjects with medical history findings will be summarized by classified data using frequency tables. The classification will be done according to the Medical Dictionary for Regulatory Activities (MedDRA) coding system using system organ class, high level terms and preferred terms. The most recent MedDRA version will be used.

6.1.4 Concomitant medication

The number of subjects that used concomitant medication will be analyzed using frequency tables based on classified data. The classification will be done according to the WHO-DD.

6.1.5 NYHA-classification

A frequency table will be created for the NYHA-classification by visit.

6.2 Efficacy

Not applicable.

6.3 Pharmacokinetics/pharmacodynamics

Not applicable.

6.4 Safety

If not stated otherwise, analyses will be performed on the FAS population.

6.4.1 Adverse Events (AEs)

Individual listings of AEs will be provided.

The incidence of AEs will be summarized by cohort using MedDRA terms.

Healthcare resources

Information regarding healthcare resources will be listed.

Serious adverse events and deaths

For serious AE outcomes, AEs leading to discontinuation and deaths, listings of subjects will be provided by cohort, subject and/or AE.

6.4.2 Vital Signs

Vital signs parameter will be summarized by cohort/total and visit using descriptive statistics including arithmetic mean, standard deviation (SD), median, minimum and maximum. Statistics will be presented for the original data and difference to baseline.

Graphical displays of individual data as well as mean values with standard deviations will be created for each parameter by cohort using planned sampling times.

6.4.3 ECG

All quantitative ECG parameters will be summarized by visit and cohort/total using descriptive statistics including arithmetic mean, SD, median, minimum, and maximum.

Graphical displays of individual data as well as mean values with standard deviations will be created for each parameter by cohort using planned sampling times.

Qualitative ECG parameters will be summarized by parameter, cohort and visit using frequency tables.

The number of subjects with QT, QTcB, and QTcF values ≤ 450 msec, $>450-480$ msec, $>480-500$ msec and >500 msec will be summarized by cohort.

6.4.4 Echocardiography

All quantitative echocardiography parameters will be summarized by visit and cohort/total using descriptive statistics including arithmetic mean, SD, median, minimum, and maximum.

Graphical displays of individual data as well as mean values with standard deviations will be created for each parameter by cohort using planned sampling times.

Qualitative echocardiography parameters will be summarized by parameter, cohort and visit using frequency tables.

6.5 Other evaluations

If not stated otherwise, analyses will be performed on the FAS population.

For each parameter (6-minute walking distance, KCCQ, PRO), subjects will be split into classes representing clinically relevant worsening versus no relevant change or improvement. The exact definition will be given in the respective subsection.

6.5.1 6-minute walking distance

The 6MWD will be summarized by visit and cohort/total using descriptive statistics including arithmetic mean, SD, median, minimum, and maximum.

A frequency table will be created for the comparison of the subjects with and without observed worsening according to the following definitions:

- Worsening: decrease in 6MWD by at least 30 meters
- No worsening: decrease in 6MWD by up to 30 meters, no change or increased 6MWD

6.5.2 Quality of life / PRO

6.5.2.1 KCCQ

The summary scores “Total Symptom Score”, “Clinical Summary Score”, and “Overall Summary Score” as well as the “Physical Limitation Scores” will be summarized using frequency counts by cohort and total.

A frequency table will be created for the comparison of the subjects with and without observed worsening according to the following definitions:

- Worsening: decrease in KCCQ score by at least 5 points
- No worsening: decrease in KCCQ score by up to 5 points, no change or increased KCCQ score

6.5.2.2 PRO

The “Overall Activity Score” will be calculated as the sum of the following mean items: walking general, housework, and exercise.

The parameters

- Overall Activity Score
 - o General physical activity item (1 unit change on weekly average score)
 - o Physical activity impression of change item (2 unit change)
 - o Fatigue impression of change item (2 unit change)
 - o Shortness of breath impression of change item (2 unit change)
 - o Swelling impression of change item (2 unit change)

will be summarized using frequency count.

In addition, response with respect to the anchor measures derived from the following individual items

- General physical activity item (1 unit change)

- Physical activity impression of change item (2 unit change)
- Fatigue impression of change item (2 unit change)
- Shortness of breath impression of change item (2 unit change)
- Swelling impression of change item (2 unit change)

will be tabulated using frequency tables.

A frequency table will be created for the comparison of the subjects with and without observed worsening according to the following definitions:

- Worsening: decrease in “Overall Activity Score” by at least 2 units
- No worsening: decrease in “Overall Activity Score” by up to 2 points, no change or increased “Overall Activity Score”

The univariate linear mixed model (LMM) for the repeated values of the “Overall Activity Score” is

$$Y_{ij} = \mu + S_i + v_j + \beta base_i + E_{ij}$$

where μ is a constant common to all observations, S_i is the normally distributed random variable with mean zero and variance σ_d^2 corresponding to subject i , v_j is the fixed effect corresponding to visit j , and E_{ij} is a normally distributed random variable with mean zero and variance σ_e^2 , independent of S_i . The variable “base” is the baseline measurement included as covariate and β is the corresponding regression parameter.

Based on the described LMM, point estimates and 90% confidence intervals for the “Overall Activity Score” will be calculated.

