#### USE OF DIARY ITEMS TO VALIDATE ACTIVITY MONITOR

- Compare 1 week of activity monitor data with physical activity items from 1 week of diary monitoring
- Average diary data over 7 day period (must have  $\geq 4$  days to calculate a value)
- Physical Activity Diary Scores
  - Overall activity including carrying/lifting, walking outside, walking general, climbing stairs, housework, and exercise (average across items)
  - Individual item scores including general physical activity item
- Examine correlations between the activity monitor movement data and the physical activity diary scores

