#### USE OF DIARY ITEMS TO CALCULATE RESPONDER DEFINITIONS

- Calculate average activity/symptom scores associated with change on anchor measures
- Anchor measures
  - General physical activity item (1 unit change on weekly average score)
  - Physical activity impression of change item (2 unit change)
  - Fatigue impression of change item (2 unit change)
  - Shortness of breath impression of change item (2 unit change)
  - Swelling impression of change item (2 unit change)
- Address using data from each weekly interval

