7.2 Changes in the planned statistical analysis

The planned analysis described in the CSP were revised comprehensively for the following reasons:

- Lower number of subjects included
- Changes in procedure schedule
- Changes of device
- Changes of parameters provided by the vendor

8. References

[1] Integrated Clinical Study Protocol No. BAY 1067197 / 19167, version 4.0, dated 21 FEB 2020

[2] Clinical Pharmacology Standards (CLIPS), version 3.0, dated 05 AUG 2020

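### The SAP scores overall activity from three of the protocol's six diary items, gives no reason specific to the score, and sets a 2-unit worsening cut not derived from the protocol's anchor items

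*SAP*

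**What the plan says.** Protocol Appendix 16.1, in the part on using the diary to validate the activity monitor, defines the score as "Overall activity including carrying/lifting, walking outside, walking general, climbing stairs, housework, and exercise (average across items"). The weekly step is "Average diary data over 7 day period", and at least four diary days are needed for a value.

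The next part of the appendix, on responder definitions, sets no cut on that score. Its method is "Calculate average activity/symptom scores associated with change on anchor measures". The anchors are the general physical activity item, with a 1-unit change in the weekly average, and four impression-of-change items with a 2-unit change each, for example "Physical activity impression of change item (2 unit change").

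In SAP 6.5.2.2 the Overall Activity Score "will be calculated as the sum of the following mean items: walking general, housework, and exercise". The SAP adds two classes. One is "Worsening: decrease in “Overall Activity Score” by at least 2 units"; the other begins "No worsening: decrease in “Overall Activity Score” by up to 2 points" and includes no change and any increase. SAP 6.5 presents such classes as separating clinically relevant worsening from the rest. The score also has its own linear mixed model with 90% confidence intervals, and SAP 6.5.4.1 runs DynaPort subgroup analyses by the worsening classes of 6MWD, KCCQ and PRO.

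SAP 7.2 gives four general reasons for revising the protocol's analyses: fewer subjects, the procedure schedule, the device, and "Changes of parameters provided by the vendor". None mentions the diary, its items or a cut-off.

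**The concern.** A reader holding both documents finds two measures of overall activity with nearly the same name and different content, and no account of the move from one to the other. Protocol 9.7.2 says the diary is completed on a tablet, and the three omitted items are still in the questionnaire printed in the current protocol. The reasons in SAP 7.2 therefore do not evidently reach them.

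The score has three uses in the SAP: a mixed model, a worsening table, and one of three splits of the DynaPort data. SAP 4.1 keeps the patch data out of the clinical database, so DynaPort is the only device whose analysis this SAP specifies for the primary objective. If the worsening class rests on a subset of items and on a cut with no derivation, a difference in steps or active time between the two classes is hard to interpret. A later trial that takes the cut as a responder definition would inherit a value that the protocol's method never produced.

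**Working it through.** No figure in the plan can be reproduced, because neither document derives the 2-unit cut. The check compares the two definitions and works out what each change does.

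1. **Items.** Protocol: carrying/lifting, walking outside, walking in general, stairs, housework, exercise (6). SAP: walking in general, housework, exercise (3). Dropped: 3 of 6, or 50%. Added: none.

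2. **Sum against average.** Let S be the sum of the three retained weekly item means. Their average is S/3. With complete items, every mixed-model estimate and confidence limit for S is three times that for the average. Only the units change. A 2-unit fall in S is a fall of 2/3 = 0.67 in the three-item average.

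3. **Item selection.** Let D be the sum of the three dropped item means. The protocol's score is A = (S + D)/6, so the change in A is (change in S + change in D)/6.
   - If S falls by 2 and D does not change, A falls by 2/6 = 0.33.
   - If D falls and S does not change, A falls and the SAP score does not move.

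   Neither score can be recovered from the other, so this change is substantive.

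4. **Origin of the cut.** The protocol's fixed changes belong to single items: 1 unit on the general activity item and 2 units on each impression-of-change item. For activity and symptom scores, it derives the value from those anchors. The SAP tabulates response on the same anchors but does not use them to derive its cut. It gives no other source for the 2 units.

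5. **Possible size, on assumptions.** The questionnaire lists response categories without numeric scores. Assume one-unit steps: 0 to 4 for each five-category time item and 0 to 10 for stairs.
   - Range of S: 3 × 4 = 12. Two units is 2/12 = 17% of it.
   - Range of A: (5 × 4 + 10)/6 = 5, or 4 if stairs is put on a 0 to 4 scale.
   - An illustrative simulation used normal item changes with mean zero, correlation 0.3 to 0.7, SD 0.5 to 1.0 category per time item, and a stairs SD 2.5 times larger. The SAP rule classed 3% to 23% of subjects as worsened. A fall of 0.67 in A, chosen only to match the per-item drop in step 2, gave a different class for 5% to 14%.

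   The 0.67 cut on A is not a protocol rule. The percentages show only that item selection can move subjects between classes; they are not estimates for this trial.

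6. **Related gaps.** A fall of exactly 2 meets both class definitions, and the SAP does not carry over the four-day minimum for a weekly mean.

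**The case against.** The case for leaving the SAP alone is a fair one. Protocol 10.1 leaves calculated variables to the SAP, and the appendix describes its own account of how the items can be used as a brief outline. The six-item average was meant for validating the activity monitor, and SAP section 2 states that the accuracy of self-reported activity against the devices cannot be meaningfully assessed. Walking outside is contained in walking in any location, stairs has 11 categories against five for the time items, and the protocol's introduction seeks non-redundant items. All analyses are exploratory, and the 6MWD and KCCQ splits are untouched.

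Much of this stands. The SAP may define the score, and there may be good grounds for dropping items. But the SAP does not state them, and those suggested here do not cover carrying/lifting, which uses the same five-category scale and is not contained in another item. None of them supplies a basis for the 2-unit cut.

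Three stronger readings are tempting and should not be adopted:

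- A reader might infer that the SAP loosened a protocol threshold, since 2 units is 2/12 = 17% of the SAP range but 2/5 = 40% of the six-item range. The protocol has no cut on its score and no worsening classes, and both percentages need an assumed coding.
- A reader might infer that the cut was borrowed from the impression-of-change items. The SAP keeps those items separately and does not say so.
- A reader might infer that the score was chosen after the data were seen, because the SAP is dated 14 APR 2021 and reports that recruitment stopped early. Protocol 10.1 requires only that the SAP be final before database lock, and nothing shows that the diary data had been examined.

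**Conclusion.** The point holds in a limited form. Three of the six items in the protocol's overall activity score are dropped without a reason specific to the score, and a 2-unit fall in what remains is called clinically relevant worsening without the anchor-based derivation that the protocol planned. Both facts can be read directly from the documents and need no assumed coding. Replacing the average by a sum is not a fault in itself when items are complete.

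The worsening classes are new in the SAP, so the departure is from the protocol's score and its method for responder values, not from any protocol subgroup. The effect on classification cannot be sized from the documents; the simulation figures depend on the stated coding and distributions. What is at stake is interpretation of the diary score and of one DynaPort split, and traceability between the two documents. The change is worth making because it is cheap and guards against the appearance of selective scoring.

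**What to change.** - Keep the SAP score. As a supplementary analysis, also compute the six-item average exactly as Protocol Appendix 16.1 defines it, from weekly means with at least four diary days. A second version with stairs on the same scale as the other items is optional and should be labelled as being in neither document.
- For the six-item score, report the same mixed model. Give its worsening table and DynaPort split using a cut derived from the anchor items, as the appendix plans. Show the anchor-based value for the SAP score beside its 2-unit cut.
- Record in SAP 7.2 why the three items were dropped, or that they were not available. If they were not available, the six-item score cannot be produced and that statement is the remedy.
- State the numeric coding and the minimum number of diary days, and assign a fall of exactly 2 to one class.

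The cost is one or two derived variables and a few tables from data the protocol already collects, plus one more exploratory score to interpret in a small sample. Two limits apply to the anchor-based cut. It will be imprecise with few subjects. The impression-of-change items as printed ask about change since hospital discharge, so the report should say which anchors were usable for ambulatory patients.

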6.5.3 Biomarker laboratory

Biomarker parameter will be summarized by cohort/total and visit using descriptive statistics including arithmetic mean, SD, median, minimum and maximum. Statistics will be presented for the original data and difference to baseline.

Graphical displays of individual data as well as mean values with standard deviations will be created for each parameter by cohort using planned sampling times.

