Plan for statistical analysis	
Statistical analyses will be of explorative and descriptive nature. The study is not aimed to confirm or reject pre-defined hypotheses.
 
All variables will be analyzed descriptively with appropriate statistical methods: categorical variables by frequency tables (absolute and relative frequencies) and continuous variables by sample statistics (i.e. mean, standard deviation, minimum, median, quartiles and maximum). Continuous variables will be described by absolute value and as change from baseline per analysis time point, if applicable.
 
The variability of biomarkers assumed to be normal distributed will be analyzed using a linear mixed effect model with subject as random factor, and time as fixed factor, possibly including additional covariates as may result from the assessment at baseline for subject stratification or as required for clinical interpretation. Based on this model, point estimates (LS-Means) and exploratory 90% confidence intervals will be calculated for comparing baseline and 3 months data. For biomarkers assumed to be log-normal distributed, the logarithms of the biomarker concentration will be analyzed, and results will be reported as ratio for comparing baseline and 3 months data.
 
All analyses will be performed for the total study population (overall analysis). Subjects wearing at least once the VitalPatch biosensor system and for which data was successfully collected over 5 days will be included in the analysis.
 
Sample size and disposition information by analysis time point will be displayed in a frequency table.

 Replacement of AVIVO MPM with VitalPatch Biosensor as per Amendment 2 (Section 15.2)

 Replacement of AVIVO MPM with VitalPatch Biosensor as per Amendment 2 (Section 15.2)

 Adapted to reflect the extension on non-hospitalized subjects as per Amendment 3 (Section 15.3)

 Adapted to reflect the limitations of the VitalPatch biosensor system as per Amendment 3 (Section 15.3)

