## **10. Statistical methods and determination of sample size**

### **10.1 General considerations - amended**

All statistical details including calculated variables and proposed format and content of tables will be detailed in the Statistical Analysis Plan (SAP). The SAP will be finalized before study database lock. Statistical analysis will be performed using SAS or R; the versions used for both types of software will be specified in the SAP.

Statistical analyses will be of explorative and descriptive nature. The study is not aimed to confirm or reject pre-defined hypotheses; however, particular attention will be given to the ejection fraction (preserved versus reduced) as stratification factor.

All variables will be summarized with appropriate statistical methods: categorical variables by frequency tables (absolute and relative frequencies) and continuous variables by sample statistics (i.e. mean, standard deviation, minimum, median, quartiles and maximum).

Continuous variables will be described by absolute value and as change from baseline per analysis time point, as applicable.

Data from VitalPatch and DynaPort devices is expected to include missing values, as result of compliance in wearing the device. The amount of missing data within a day cannot be predicted and will be an outcome of the study. Missing data within day will be assessed by vendors according their validated algorithms of data pre-processing and quality check. No imputation will be performed in case day monitoring did not pass quality checks. The amount of missing monitoring will be assessed prior each statistical analysis and in presence of outliers the exclusion of subjects' data may occur.

All analyses will be performed for the FAS population (overall analysis) and separately for each participating country if subject numbers are sufficient and if required for local reasons.

Sample size and disposition information by analysis time point will be displayed in a frequency table.

All therapies documented will be coded using the World Health Organization – Drug Dictionary. Medical history, any diseases and AEs will be coded using the latest Medical Dictionary for Regulatory Activities (MedDRA) version.

No interim analyses are planned. The final analysis will be performed after end of the study which is the date the analytical dataset is completely available.

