### 10.3.3 Analysis of primary and secondary outcomes

#### 10.3.3.1 Assessment of variability

The variability between subjects and within subjects across time for each of the parameters of interest will be described using a linear mixed model (LMM) with subject as random factor, and time as fixed factor, possibly including additional covariates as may result from the assessment at baseline for patient stratification or as required for clinical interpretation.

In addition to effects and interactions of fixed effects parameters LMMs will be used to estimate simultaneously parameters of the variance and covariance components of random effects due to subjects.

The LMM for the parameter of interest (Y) as selected among the molecular and digital biomarkers available (i.e. laboratory parameters and device generated digital data) will have the following base annotation:

$$Y_{st} = \beta_0 + \beta_1 \cdot TIME_t + S_{0s} + \varepsilon_{st}$$

Where S is subject (random) and TIME represents visit, with baseline as reference.

The HF type (preserved/reduced) will be included in the model (here denoted as C), as random factor, and the effect on intercept or slope will be assessed:

$$Y_{st} = \beta_0 + (\beta_1 + C_{1s}) \cdot TIME_t + S_{0s} + C_{0s} + \varepsilon_{st}$$

Where  $C_{1s}$  will be the effect of HF type on the slope (e.g., if changes in physical activity are different between the two sub-populations) and  $C_{0s}$  will be the effect on the intercept (e.g., if the two sub-populations have different baseline values).

Given the high number of parameters involved and the exploratory nature of the study, all of the possible models will not be addressed here, and the base model will be extended as appropriate depending on the specific question to address and the given subset of parameters involved.

Testing of random effects and visualization of residuals will be performed in order to highlight single subjects (or sub-group) showing outstanding or peculiar characteristics.

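### SAP 6.5.3 leaves out, without a specific reason, the log-scale analysis and ratio with 90% CI that the protocol plans for biomarkers assumed log-normal

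*SAP*

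**What the plan says.** **Protocol.** The plan for statistical analysis in the synopsis has two parts, depending on the assumed distribution. For normal markers: "The variability of biomarkers assumed to be normal distributed will be analyzed using a linear mixed effect model with subject as random factor". From that model, LS-means and "exploratory 90% confidence intervals will be calculated for comparing baseline and 3 months data". For the others: "For biomarkers assumed to be log-normal distributed, the logarithms of the biomarker concentration will be analyzed, and results will be reported as ratio". Section 10.3.3.1 confirms that blood markers are covered, since the modelled variable is to be taken "as selected among the molecular and digital biomarkers available (i.e. laboratory parameters and device generated digital data". Section 10.1 separately prescribes ordinary descriptive statistics for every continuous variable: "Continuous variables will be described by absolute value and as change from baseline per analysis time point, as applicable".

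**SAP.** Section 6.5.3 is the only place that states an analysis for the laboratory markers: "Biomarker parameter will be summarized by cohort/total and visit using descriptive statistics including arithmetic mean, SD, median, minimum and maximum". Then: "Statistics will be presented for the original data and difference to baseline". Then: "Graphical displays of individual data as well as mean values with standard deviations will be created for each parameter by cohort using planned sampling times". Mixed models appear in the SAP only for the PRO Overall Activity Score (6.5.2.2) and the DynaPort parameters (6.5.4.1), both with 90% confidence intervals. Section 7.2 says that the protocol's analyses were comprehensively revised. Its reasons are fewer subjects and changes in schedule, device and vendor parameters.

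**The concern.** The protocol describes this as a pilot that should supply baseline values and standard deviations for planning later trials (section 5, Justification of the design, with activity measures as the example). Section 10.3.3.1 extends the variability assessment to laboratory parameters. Evaluating hs-copeptin is still listed in SAP section 2 and is not among the objectives footnoted there as dropped.

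If a marker is roughly log-normal, later planning needs its geometric level, its spread on the log scale and the proportional change with an interval. SAP 6.5.3 supplies none of these. The mean and SD of the difference, with the count of observations from SAP 4.1, would let a reader work out an interval for the absolute change. No such arithmetic recovers the within-subject ratio. The quotient of two visit medians is a different quantity and has no interval.

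**Working it through.** There is no power or precision figure to reproduce, because protocol 10.4 states that no power modelling was done. The check therefore has a textual part and an illustrative part.

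**1. Text side by side, for a marker assumed log-normal**

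| Element | Protocol (synopsis, 10.1, 10.3.3.1) | SAP 6.5.3 |
|---|---|---|
| Arithmetic mean, SD, median, range | yes | yes |
| Change from baseline, original scale | yes | yes |
| Log scale | yes | no |
| Ratio, 3 months to baseline | yes | no |
| Mixed model | yes | no |
| 90% CI | yes | no |

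The first two rows agree. The last four are missing from the SAP.

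**2. Do the SAP 7.2 reasons explain the gap?** Device and vendor changes do not affect central-laboratory assays. The schedule still has blood samples at visits 1 and 4 (protocol Table 9-1; SAP section 3), so the baseline-to-3-month ratio can be estimated. Fewer subjects could be a reason to drop a model, but the same SAP keeps two mixed models with 90% CIs in the same small study.

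**3. How far skewness matters.** The documents give no spread for any marker. Let s be the SD of ln concentration, an assumption taken from 0.3 to 1.2. For a log-normal variable, arithmetic mean / geometric mean = exp(s²/2):

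- s = 0.3: exp(0.045) = 1.05
- s = 0.5: exp(0.125) = 1.13
- s = 0.8: exp(0.32) = 1.38
- s = 1.0: exp(0.50) = 1.65
- s = 1.2: exp(0.72) = 2.05

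**4. Influence of the two highest values.** These are median changes when the two highest values are removed, from 20,000 simulated log-normal samples. The sample sizes are the target cohort sizes (HFrEF 20, HFpEF 60).

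| n | s | mean | SD | geometric mean | median |
|---|---|---|---|---|---|
| 20 | 0.3 | -6% | -22% | -5% | -3% |
| 20 | 0.8 | -20% | -37% | -13% | -8% |
| 20 | 1.0 | -26% | -43% | -16% | -10% |
| 20 | 1.2 | -32% | -49% | -19% | -12% |
| 60 | 0.8 | -10% | -25% | -6% | -3% |
| 60 | 1.2 | -19% | -36% | -8% | -4% |

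Removing the top two values shrinks any SD, even with mild skew (22% at s = 0.3, n = 20). Only the excess over that is due to skewness.

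**5. Detecting a proportional change.** Further assumptions, also not in the documents: a true 20% fall, correlation 0.7 between visits on the log scale, and the same s at both visits. Entries are the percentage of 40,000 simulated studies in which a paired 90% CI excludes no change, log scale v original scale.

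| n | s = 0.5 | s = 0.8 | s = 1.0 | s = 1.2 |
|---|---|---|---|---|
| 20 | 80 v 74 | 46 v 36 | 34 v 24 | 28 v 18 |
| 40 | 97 v 94 | 72 v 57 | 56 v 37 | 44 v 26 |
| 80 | 100 v 100 | 94 v 81 | 82 v 57 | 68 v 39 |

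At s = 0.3 the two scales are practically equal at all three sizes. The gap is about 10 points at n = 20 and 13 to 29 points at n = 80, for s from 0.8 to 1.2.

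**The case against.** **The arithmetic summaries are not a departure.** A reader might infer that SAP 6.5.3 contradicts the protocol by using means, SDs and differences. It does not: protocol 10.1 prescribes these for all continuous variables. This stands, and it limits the point to what is missing.

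**The protocol rule is conditional.** A reader might infer that the documents declare NT-proBNP, hs-copeptin and hs-TnT log-normal. They do not. The synopsis provides for both distributions and assigns no marker to either, so skewness and its size remain assumptions. Even so, the SAP carries out neither part: markers assumed normal lose their model and interval too.

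**The SAP output is partly robust.** Median, minimum and maximum are planned for level and for change, along with displays of individual data, so extreme subjects would be visible. This stands. It does not supply a ratio or an interval.

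**No power is lost in any formal sense.** A reader might take the n = 80 row above as the study's loss. The documents do not support that. SAP section 2 says recruitment stopped early and gives no number of subjects, SAP 6.5.3 plans no interval or test, and the study is exploratory. At n = 20 the log analysis would itself miss the assumed change in most studies when s is 0.8 or more. The table only shows how the two scales compare.

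**The analysis may be described elsewhere.** SAP 4.1 sends patch data to biomarker analyses that it does not describe, and it relies on a sponsor standard that is not available here. Neither is said to cover log-scale analysis of blood markers. If one does, the SAP should say so.

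**SAP 7.2 announces a comprehensive revision.** It does, and fewer subjects is a conceivable reason for less modelling. But the retained PRO and DynaPort models weaken that reason, and a small sample gives single extreme values more weight.

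**Conclusion.** The omission is established from the text: log scale, ratio, mixed model and 90% CI are in the protocol and absent from SAP 6.5.3, with no specific reason given. The consequence is conditional. If a marker's ln-SD is about 0.8 to 1.2, its arithmetic mean is 1.4 to 2.1 times its geometric mean, and two subjects in 20 can carry 20% to 32% of the mean. If it is near 0.3, little changes. In either case the planned output gives no proportional change with an interval. No error rate or sample size is affected, so this is a moderate gap in an exploratory analysis that is cheap to close.

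**What to change.** In SAP 6.5.3:

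- State for each marker whether it is treated as log-normal.
- For log-normal markers, keep the present summaries and add geometric mean and geometric CV by visit and cohort, and the ratio of visit 4 to baseline with a 90% CI from the protocol's mixed model on log values.
- If the number of subjects is too small for the model, use a paired analysis of log differences, back-transformed. With two time points and complete pairs this normally gives the same estimate as the random-intercept model.
- Plot these markers on a log axis.

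If the sponsor prefers to leave the analysis out, SAP 7.2 should record the omission and its reason. If detection rates are quoted in support, show them over a range of sample sizes below 80, with the correlation and the size of the fall labelled as assumptions.

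The cost is SAP wording and routine programming. No further samples or visits are needed. At a small sample size the interval may be wide, and the report should say so.
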